10.2. General

Statistical comparisons will be performed using two-sided significance tests and two-sided confidence intervals. Statistical comparisons of the two randomized groups with respect to primary and secondary clinical endpoints will be based on time-to-event analyses. In the time-to-event analyses, all available follow up information will be used. Recurrent events will be ignored in the primary analysis but will be analyzed in planned secondary manuscripts. Follow up will begin at the time of randomization and will be considered to be censored at the time of each participant’s last study visit for those participants not having an event of interest. The occurrence and timing of clinical endpoint events in the primary analysis will be based solely on CEC adjudicated endpoint data. Unless otherwise stated, references to the non-fatal myocardial infarction (MI) event will refer to the Primary MI Definition (see Section 10.1 for details).

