7.2. Methods for Handling Missing Data

Every effort will be made to obtain complete data. In the unlikely event that there is missing data, rules on how to handle the missing data will be used. These rules for how to handle the missing data will be discussed in appropriate places in the analysis plan below. Further details on how missing data will be handled can be found in the SAP Appendix for Definitions and Reporting Conventions.

In general, all available data will be included in data listings and tabulations. Population denominators will be displayed in column headers. Individual denominators will be displayed for each summary such that the amount of missing values will be evident. Participants who withdraw from the study or are lost to follow-up will still be included in the denominators for any proportions where data are available prior to study withdrawal or when the participant is lost to follow up.

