In addition to Cox regression, cumulative endpoint event rates will be estimated as a function of follow-up time in each treatment group using Kalbfleisch & Prentice's nonparametric estimator of the cumulative incidence function (CIF) [6]. The Kalbfleisch & Prentice CIF estimator is equivalent to the Kaplan-Meier[7] estimator when applied to endpoints that are not subject to competing risks. It was selected for this study in order to account for the competing risk of non-cardiac deaths in the analysis of the primary endpoint and the occurrence of any type of death in the analysis of individual non-fatal endpoints. Cumulative endpoint event rates and differences in cumulative endpoint event rates for INV versus CON at yearly time points will be estimated and presented with 95% confidence intervals. These non-parametric analyses are important for descriptive purposes, to assess overall clinical impact, and will be a focus of interpretation if the event rate curves cross [8, 9]. These non-parametric analyses may also be used to construct summary measures of treatment effect which are interpretable when the proportional hazards assumption is violated. [9, 10]

In addition to comparing overall outcomes for the two randomized groups, we will perform additional analyses to assess whether the treatment effect varies according to pre-specified participant baseline characteristics, as described in Section 10.6 below.

Finally, as a sensitivity analysis, the analyses described in this section will be repeated in the Protocol Version 2.0 population and the core-lab ischemia population, as defined in Section 6.2 and 6.3 above.

10.4.1. Cox model for primary endpoint analysis.

As noted above, analysis of the primary endpoint will be adjusted for covariates and will be performed using the framework of Cox regression. Pre-specified covariates will consist of the following:

- Age
- Sex
- Estimated glomerular filtration rate (eGFR)
- Ejection fraction
- Diabetes

Covariates were selected on the basis of their established prognostic importance in other SIHD cohorts, highly complete data capture, and a sufficient range of values for risk to vary among participants meeting trial eligibility criteria. The following definitions and data handling conventions will be adopted:

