- Cumulative incidence of revascularization for any other reason (non-adherence)
 - All
 - Occurring before participant’s first primary endpoint event

Incidence rates for each quantity listed above will be estimated using the cumulative incidence function method for competing risks data.[6] Participant follow-up will be censored at the last contact date or terminated after the participant’s death date, whichever occurs first. For estimating rates of catheterization and revascularization prior to endpoint events, occurrence of an endpoint event will be regarded as a competing risk. Reasons for catheterization will be based on the site-reported indication for the catheterization procedure as captured on the SITECATH1 form of the e-CRF. If one of the site-reported indications for the catheterization procedure includes MI, resuscitated cardiac arrest, or worsening or new onset heart failure, then the catheterization will be classified as “catheterization for a suspected acute event”. Otherwise, if one of the site-reported indications is “Failure of OMT/Refractory angina” then the catheterization will be classified as “catheterization for OMT failure/refractory angina”. Otherwise, if neither of the above conditions is met, the catheterization will be considered to be non-adherent to the CON strategy. Primary endpoints include MI, hospitalization for heart failure, hospitalization for unstable angina, and resuscitated cardiac arrest and will be based on best available data (i.e. adjudicated endpoints, if available, otherwise unadjudicated data will be used) while event adjudication is in progress. Endpoints occurring on the same day as catheterization or revascularization will be considered to occur before the catheterization or revascularization unless the endpoint was a PCI-related or CABG-related MI.

The main goal of the analyses described above is to monitor the frequency of transitions from the state of "no post-randomization catheterization" to "at least 1 post-randomization catheterization" in CON participants. Transitions occurring before the participant's first primary endpoint event are of particular concern because these have the potential to dilute power for the primary endpoint. Transitions occurring after a confirmed primary endpoint event will not dilute power because the endpoint is already counted.

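### Does censoring event-free participants at the last study visit, with no stated closing date for adjudicated events, bias the primary results?

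*SAP*

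**What the plan says.** Four parts of the SAP bear on the point.

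- **Section 10.2** makes a general promise: "In the time-to-event analyses, all available follow up information will be used". Follow-up starts at randomization and is censored at the "last study visit for those participants not having an event of interest". On events it says: "The occurrence and timing of clinical endpoint events in the primary analysis will be based solely on CEC adjudicated endpoint data". It defines neither the last visit nor a closing date for events.
- **Section 11.3** has two parallel adherence analyses. The one for the invasive arm (11.3.1) censors at the last visit. The one for the conservative arm (11.3.2) reads "Participant follow-up will be censored at the last contact date or terminated after the" death date, whichever is earlier.
- **Section 7.2** treats missing data as unlikely but provides for it: "Participants who withdraw from the study or are lost to follow-up will still be included in the denominators" of proportions where earlier data exist. It refers further rules to the SAP Appendix for Definitions and Reporting Conventions.
- **Section 10.4** chooses a cumulative incidence estimator "in order to account for the competing risk of non-cardiac deaths in the analysis of the primary endpoint". It plans that "differences in cumulative endpoint event rates for INV versus CON at yearly time points will be estimated", and says that these analyses "will be a focus of interpretation if the event rate curves cross".

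**The concern.** An estimate of incidence needs the same end date for events and for time at risk. If events are accepted whenever the committee confirms them, but event-free people leave the risk set at their last visit, the numerator can run on after the denominator has stopped. The error has one direction: estimated incidence rises.

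The reference in Section 11.3.2 to a contact date suggests that the trial holds a date later than the last visit for some people. Withdrawals and losses are provided for, so a final visit for everyone cannot be taken for granted. Section 10.2, read literally, would also censor a participant who died of a non-cardiovascular cause at the last visit rather than at death.

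Yearly incidence matters here. It becomes the focus of interpretation if the curves cross, and Section 10.4.2 gives it more weight under non-proportional hazards. If the gap between last visit and last information differed by arm, the primary hazard ratio could shift as well.

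**Working it through.** **Step 1: the wording.** Using all available follow-up most naturally means no truncation at a fixed horizon, which fits the refusal in Section 10.11 to censor at crossover. Censoring each event-free person at the last assessment is compatible with that, so Section 10.2 does not contradict itself. Sections 11.3.1 and 11.3.2 describe the same kind of analysis in the two arms and give no reason for different end dates. Loose use of two terms for one date is at least as likely as two distinct dates.

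**Step 2: the plan's own precision.** SAP Section 4 gives a margin of 1.17 with 5,179 participants. Under 1:1 allocation, events = 4/(ln 1.17/1.96)² = 4/(0.1570/1.96)² = 623.

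**Step 3: calibration.** Enrollment from October 2012 to December 2017 and follow-up to June 2019 (Section 4, the latter a power assumption) give follow-up of 1.5 to 6.7 years. Assumptions not in the documents: uniform accrual, non-cardiovascular death 0.7% a year, 20% of first events cardiovascular deaths, visits every six months, a close-out visit for all who still attend, and exponential visit-stopping. An event rate of 0.0321 a year reproduces 623 events. The true 4-year incidence is then (0.0321/0.0391) × (1 − e^(−4×0.0391)) = 11.9%.

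**Step 4: equal visit-stopping, no treatment effect.** *Literal* counts every event found but ends event-free time at the last visit. *Matched* counts the same events and ends event-free time when status was last known.

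| Stopping per year (stopped before cut-off) | Still in contact | 4-year incidence, literal | Matched |
|---|---|---|---|
| 0% | n/a | 11.9% | 11.9% |
| 1% (4.0%) | half | 12.02% | 11.90% |
| 1% | all | 12.13% | 11.90% |
| 2% (7.8%) | none, no late events learned | 11.9% | 11.9% |
| 2% | half | 12.14% | 11.91% |
| 2% | all | 12.36% | 11.90% |
| 3% (11.5%) | half | 12.27% | 11.91% |
| 3% | all | 12.61% | 11.90% |

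A hand check of the row for 2% and half in contact: 608.7 events over 18,529 person-years is 3.29% a year; over 18,960 it is 3.21%, the true rate. The 431 missing person-years inflate the rate by 2.3%. Precision is the same under both rules: exp(1.96 × √(4/608.7)) = 1.172.

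**Step 5: compare with sampling error.** One-arm half-width at 4 years, ignoring censoring: 1.96 × √(0.118 × 0.882/2590) = 1.24 points. The overstatement is 0.12 to 0.71 points. The hazard ratio stays within 0.001, and the risk difference is unchanged, because both arms move together.

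**Step 6: unequal stopping.** With 3% a year in the conservative arm and 1.5% in the invasive arm, a true hazard ratio of 1 is estimated as 0.980 rather than 0.998 (half in contact), or 0.965 rather than 0.999 (all in contact). With the arms reversed it is 1.016 rather than 0.998, or 1.034 rather than 0.999. These shifts are 11% to 22% of ln 1.17.

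**Step 7: non-cardiovascular deaths.** At 0.7% a year over 623/0.0321 ≈ 19,408 person-years there are about 136 such deaths. With six-monthly visits the mean gap is 0.25 years, so literal censoring loses 136 × 0.25 = 34 person-years, or 0.2% of the total.

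**The case for a change.** The strongest case is that Section 10.2 leaves a real gap. It does not point to an appendix for censoring, two programmers could derive different dates, and a few sentences would settle the matter before unblinding without losing an event. Harsher assumptions also give larger effects. Suppose everyone has a gap before the end of follow-up and every event in it is captured. With a true 4-year rate of 15%, a mean gap of 3 or 6 months then gives 15.7% or 16.3% at 4 years, and 23.5% or 26.5% at 6 years against a true 21.6%. With mean gaps of 6 months in the conservative arm and 3 in the invasive arm, a null hazard ratio falls to about 0.93 to 0.95.

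The missing definition stands. The harsher figures do not describe a likely analysis: complete capture of events throughout the gap means that people were still being followed, so their event-free status was known too, and no sensible analyst would discard it. Even there, the 4-year excess of 0.7 to 1.3 points lies within a half-width of 1.96 × √(0.15 × 0.85/2590) = 1.38 points. No part of the documents suggests an arm difference, and the visit-completion summaries by treatment in Section 11.2, which are repeated for the final analysis, would help show one.

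A rewritten rule would also gain little. If endpoint status is established at visits, censoring at last known status is the existing rule. Nor does it cure events learned only by chance from people out of contact: at 2% a year, with none in contact and half of the late events learned, both rules give 12.13%.

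**Conclusion.** No change is needed. Section 10.2 leaves three details open: what counts as the last visit, the closing date for events, and the Cox censoring date for a non-cardiovascular death. The ordinary way to fill them is one end date for events and time at risk, with deaths at their date, and that removes the distortion.

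Under the literal reading with equal gaps, 4-year incidence would be overstated by 0.12 to 0.71 points, below the half-width of at least 1.24 points, and the primary hazard ratio and risk difference would be essentially unaffected. A shift in the hazard ratio needs unequal gaps, for which the documents give no evidence. All these sizes rest on assumed visit-stopping and contact rates.

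The Definitions and Reporting Conventions appendix and the full protocol, with its visit schedule and close-out, are not in the text reviewed and may already settle the point. If visits include every contact, or a close-out visit covers everyone, there is no gap.

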10.3. Primary and secondary clinical endpoints

The primary endpoint of this study is the composite of CV death, non-fatal myocardial infarction (MI), hospitalization for unstable angina, hospitalization for heart failure, or resuscitated cardiac arrest as evaluated in the ITT population. The study's original protocol defined the primary endpoint as the composite of CV death or MI. The primary endpoint was reverted from the 2-item composite to the original grant peer-reviewed and current 5-item composite in June 2017 after following a protocol-defined process and receiving input from an NHLBI-convened independent Advisory Panel (see Section

11.5 and the SAP Appendix for Contingency Plan for Insufficient Primary Endpoint Events for details, with approval of the Director of the NHLBI).

Protocol-defined secondary endpoints are:

- (a) Composite of cardiovascular death or non-fatal MI
- (b) Angina control as measured by the Seattle Angina Questionnaire
- (c) Disease-specific quality of life as measured by the Seattle Angina Questionnaire
- (d) Composite of cardiovascular death, non-fatal MI or stroke
- (e) All-cause death
- (f) Cardiovascular death
- (g) Myocardial infarction
- (h) Resuscitated cardiac arrest
- (i) Hospitalization for unstable angina
- (j) Hospitalization for heart failure
- (k) Stroke
- (l) Composite of cardiovascular death, non-fatal MI, stroke, hospitalization for unstable angina, heart failure or resuscitated cardiac arrest

Additional pre-specified secondary endpoints are:

- (m) MI as determined by the CEC Charter's secondary MI definition
- (n) Composite of cardiovascular death or complicated MI as defined in the CEC charter
- (o) Complicated MI as defined in the CEC charter

Other endpoints for supportive analyses to aid interpretation of the trial's primary and secondary analyses include:

- (p) Composite of all-cause death or nonfatal MI
- (q) Composite of all-cause death, nonfatal MI, or stroke
- (r) Composite of all-cause death, nonfatal MI, or hospitalization for resuscitated cardiac arrest, unstable angina or heart failure
- (s) Composite of all-cause death, nonfatal MI, stroke, hospitalization for unstable angina, heart failure or resuscitated cardiac arrest

For the analysis of MI and for composite endpoints that include MI as a component endpoint, analysis will be based primarily on the CEC Charter's primary MI definition and secondarily on the CEC Charter's secondary MI definition. Additional definitions of MI using criteria to categorize large infarctions are expected to be developed and reported in secondary manuscripts but are not included in the current statistical analysis plan.

10.4. Analysis of the primary endpoint

Time from randomization to the first occurrence of the primary endpoint will be compared between treatment groups using the statistical framework of Cox regression [2]. As described below in this section, estimation of event rates with 95% confidence intervals not assuming proportional hazards will be performed as an important secondary analysis. To preserve power and generalizability in the face of outcome heterogeneity due to variation across participants in important baseline variables [3-5], the Cox

model for each endpoint will be adjusted for a set of prognostically important baseline covariates, to include age, sex, estimated glomerular filtration rate (eGFR), ejection fraction, and diabetes, as detailed in Section 10.4.1 below. Ties in event times will be handled using Efron's approximation.

Multiple endpoint events in the same participant, such as a recurrent non-fatal event, will not be considered in the primary results analysis, but will be analyzed in planned secondary analyses.

The hazard ratio from the covariate-adjusted Cox model will be reported along with its two-sided 95% Wald-type confidence interval, and the associated p-value will be the primary measure of statistical significance. The half width of this confidence interval is expected to be 1.17 under the null hypothesis of identical covariate-specific time-to-event distributions. The critical value required for declaring endpoint differences to be statistically significant at the 0.05 level will depend on the exact timing of interim analyses, as described in Section 11.4 below.

In addition to Cox regression, cumulative endpoint event rates will be estimated as a function of follow-up time in each treatment group using Kalbfleisch & Prentice's nonparametric estimator of the cumulative incidence function (CIF) [6]. The Kalbfleisch & Prentice CIF estimator is equivalent to the Kaplan-Meier[7] estimator when applied to endpoints that are not subject to competing risks. It was selected for this study in order to account for the competing risk of non-cardiac deaths in the analysis of the primary endpoint and the occurrence of any type of death in the analysis of individual non-fatal endpoints. Cumulative endpoint event rates and differences in cumulative endpoint event rates for INV versus CON at yearly time points will be estimated and presented with 95% confidence intervals. These non-parametric analyses are important for descriptive purposes, to assess overall clinical impact, and will be a focus of interpretation if the event rate curves cross [8, 9]. These non-parametric analyses may also be used to construct summary measures of treatment effect which are interpretable when the proportional hazards assumption is violated. [9, 10]

In addition to comparing overall outcomes for the two randomized groups, we will perform additional analyses to assess whether the treatment effect varies according to pre-specified participant baseline characteristics, as described in Section 10.6 below.

Finally, as a sensitivity analysis, the analyses described in this section will be repeated in the Protocol Version 2.0 population and the core-lab ischemia population, as defined in Section 6.2 and 6.3 above.

10.4.1. Cox model for primary endpoint analysis.

As noted above, analysis of the primary endpoint will be adjusted for covariates and will be performed using the framework of Cox regression. Pre-specified covariates will consist of the following:

- Age
- Sex
- Estimated glomerular filtration rate (eGFR)
- Ejection fraction
- Diabetes

Covariates were selected on the basis of their established prognostic importance in other SIHD cohorts, highly complete data capture, and a sufficient range of values for risk to vary among participants meeting trial eligibility criteria. The following definitions and data handling conventions will be adopted:

- Age will be computed as the difference in years between the participant's date of birth and randomization date as collected in the IXRS. The date of birth is only entered in the e-CRF in the event that the date of birth information entered in the IXRS system at the time of enrollment is incorrect. If the IXRS system information is correct, then the date of birth as entered into the IXRS system at the time of enrollment will be used. Otherwise, the e-CRF entered date of birth will be used.
- Sex will be based on data collected in the DEMOGRAPHICS section of the e-CRF. In the unexpected event of missing data, the participant's sex will instead be obtained from information entered in the IXRS system at the time of enrollment.
- Estimated glomerular filtration rate (eGFR) will be calculated according to the 1999 Modification of Diet in Renal Disease (MDRD) formula using data captured in the DEMOGRAPHICS and MEDICAL HISTORY sections of the e-CRF. The formula is:
$$\text{eGFR} = 186.3 \times \text{SerumCr}^{-1.154} \times \text{age}^{-0.2013} \times 1.212(\text{if participant is black}) \times 0.742(\text{if female})$$
where SerumCr denotes serum creatinine in mg/dL, and age denotes the participant's age in years. eGFR values will be obtained from information entered in the IXRS system at the time of enrollment or from data entered in baseline CRF's if the IXRS-entered value is unavailable.
- Ejection fraction will be based on the site-reported value if available and on the core-lab entered value if the site-reported value is unavailable. Because missing data was anticipated in the design phase, the e-CRF was structured to capture ejection fraction as a categorical variable in participants for whom the categorical value is known but the continuous value is unknown. Categorical ejection fraction data will be incorporated in a multiple imputation procedure in order to impute continuous ejection fraction values in participants with only categorical values entered.
- Diabetes will be modeled as a simple indicator (yes/no) and will be based on data collected in the DEMOGRAPHICS section of the e-CRF.

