In February 2018, power was re-estimated for the study's revised primary endpoint (5-item composite) using updated event rate assumptions and assuming that participants would be followed until June 2019. The final sample size of 5,179 participants was estimated to provide 80% power to detect an 18.5% relative reduction in the 4-year rate of the 5-item primary composite endpoint. This sample size would also allow estimation of the hazard ratio to within a multiplicative margin of error of 1.17 with 0.95 confidence.

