10.4.2. Modeling of continuous variables

To allow for non-linear covariate effects, the continuous variables of age, ejection fraction and eGFR will be modeled as restricted cubic splines with knots at the approximate 10th, 50th, and 90th percentiles of each variable's empirical distribution.

The proportionality assumption of the Cox model will be assessed by examining log-log survival plots and by adding a time-dependent covariate to the Cox model representing the interaction between treatment and time. If this interaction is large and statistically significant, then there is evidence of non-proportionality. In that case, a cautious interpretation of the Cox model hazard ratio will be encouraged, and non-parametric event rate estimates will be emphasized.

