11.3. Adherence to assigned treatment strategy

11.3.1. Use of catheterization and revascularization in INV

The INV strategy mandates use of early catheterization within a target of 30 days after randomization and revascularization soon thereafter, if appropriate, based upon coronary anatomy and other clinical considerations. To assess adherence to these requirements, the distributions of time from randomization to catheterization and time from randomization to revascularization will be estimated using the cumulative incidence function method for competing risks data.[6] For this analysis, participant follow-up will be censored at the date of last study visit. Death prior to catheterization or revascularization will be regarded as a competing risk. The cumulative proportion of participants receiving catheterization and revascularization will be estimated at specific time intervals (e.g. 30 days post randomization) both overall and within subgroups (e.g. prior CABG). For participants not undergoing catheterization by the time of the six-week and 3 month visits, the site-reported reason for no catheterization will be tabulated based on CRF-defined categories (participant preference, physician preference, intercurrent illness, participant died, other, unknown). For participants with site-reported planned medical therapy following catheterization, the reason for planned medical therapy will be tabulated according to CRF-defined categories (no obstructive CAD, anatomy not suitable for any mode of revascularization, participant preference, other).

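### Do the loosely worded triggers for emphasising non-parametric event rates (SAP 10.4 and 10.4.2) need tighter definition?

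*SAP*

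**What the plan says.** Two places in the SAP say when non-parametric estimates move to the foreground.

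- **Section 10.4** plans yearly cumulative incidence estimates and between-arm differences with 95% confidence intervals, and says these analyses "will be a focus of interpretation if the event rate curves cross". It sets no time window or minimum separation for a crossing.
- **Section 10.4.2** checks proportional hazards with log-log survival plots and by "adding a time-dependent covariate to the Cox model representing the interaction between treatment and time". It continues: "If this interaction is large and statistically significant, then there is evidence of non-proportionality". The consequence is that "a cautious interpretation of the Cox model hazard ratio will be encouraged, and non-parametric event rate estimates will be emphasized". It gives no function of time, no level for this check, no value for large, and no decision rule for the plots.

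Neither section says which condition governs if only one is met, and neither refers to an appendix on this point. The SAP appendices are not in the supplied text, and the supplied protocol is an addendum only. A convention elsewhere therefore cannot be excluded.

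Other sections limit what is at stake. Section 10.4 makes the p-value from the adjusted Cox model the primary measure of significance. Section 10.9 tabulates cumulative incidence yearly with pointwise intervals. Section 10.12 commits to conservative interpretation of secondary analyses.

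**The concern.** Crossing curves are foreseeable in this trial. In the invasive (INV) arm, "The INV strategy mandates use of early catheterization within a target of 30 days after randomization", and under Section 10.1 infarctions after PCI or CABG count in the primary MI definition. An early INV excess followed by a later advantage over the conservative (CON) arm would make the Cox hazard ratio an average of opposing effects. The caution in Section 10.4.2 is the safeguard against over-reading that average.

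If the time scale of the test is chosen after the curves are seen, whether readers get that caution could depend on the choice. Observed curves can also cross by chance when hazards are proportional, so the two triggers can point in different directions. The risk is selective emphasis in the primary report.

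**Working it through.** **1. The plan's own figures, which fix the event count.** Section 10.4 states: "The half width of this confidence interval is expected to be 1.17". With 1:1 allocation, events D = 4 × (1.96 / ln 1.17)² = 4 × (1.96 / 0.1570)² ≈ 623. Section 4 gives 80% power for an "18.5% relative reduction in the 4-year rate of the 5-item primary composite endpoint" with 5,179 participants, but not the CON rate p. Take HR = ln(1 − 0.815p) / ln(1 − p) and power = Φ(½√D × |ln HR| − 1.96):

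- p = 14% (assumed): HR = 0.803; 12.48 × 0.219 − 1.96 = 0.77; power 78%.
- p = 20% (assumed): HR = 0.797; 12.48 × 0.226 − 1.96 = 0.87; power 81%.
- p = 10-13% (assumed): power 76.4-77.7%. With 659 events, the most that still rounds to a 1.17 margin, power is about 79% or more over 10-20%.

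The stated figures reproduce within about 2 points for p of 14-20%, so roughly 620-660 events is the right scale.

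**2. What the triggers change.**

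| Item | Depends on a trigger? |
|---|---|
| Primary p-value (adjusted Cox) | No (10.4) |
| Hazard ratio and its interval | No (10.4) |
| Yearly rates and differences with intervals | No (10.4, 10.9) |
| Emphasis on the yearly estimates | Yes, either trigger |
| Added caution on the hazard ratio | Yes, 10.4.2 only |

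**3. Simulation under proportional hazards.** Assumptions: 5,179 participants, uniform accrual, follow-up about 1.4-6.7 years (October 2012 to the end of 2017, closing June 2019), exponential baseline, unadjusted Cox model, 4-year rate about 12% (626 events). Large is ignored because it has no value.

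- HR 1.0: curves cross between 6 months and 5 years in about 80-84% of trials. The interaction test rejects in 3-6% on either time scale.
- HR 0.815: curves cross after 6 months in 33-35%, at yearly points in 12-13%, and by at least 0.5 points each way in 6-7%. The test rejects in about 5%.

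**4. Simulation with early excess.** Assumed 1.5-2% INV excess in the first 60 days, later HR 0.80-0.85, 4-year rate 12-15%:

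- Mean Cox HR is 0.90-1.01. The mean INV minus CON difference is +0.7 to +1.5 points at year 1 and −0.4 to −2.2 at year 5.
- The linear-time test rejects in 52-86% and the log-time test in 95-100%. The two disagree in 14-43%.

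**5. How often both triggers fail.** Either trigger brings the non-parametric estimates forward, so the relevant figure is the share of trials in which neither fires. In the step 4 scenarios, using linear time, this is 0.2-6%, or 1-12% if a crossing needs 0.5 points each way.

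Three other assumed shapes with a true crossing (HR 1.5 or 2.0 to 6 months, or 1.3 to 1 year, then 0.8) give a similar result. Neither = 1 − (exactly one fires) − (both fire), with linear time and crossing after 6 months:

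- HR 1.5: 1 − 0.637 − 0.344 = 1.9%
- HR 2.0: 1 − 0.320 − 0.662 = 1.8%
- HR 1.3: 1 − 0.485 − 0.490 = 2.5%

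Requiring 0.5 points each way gives 12.9%, 5.1% and 10.9%.

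**6. Would a fixed time function be better?** For an assumed benefit starting at year 2 (HR 0.65-0.75), linear time rejects in 33-55%, log time in 24-43%, and a 2-df test of both in 24-45%. The ranking reverses from step 4.

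**The case for a change.** The strongest case for a change is that naming the time function, the level and the meaning of large costs a few words and removes a choice made with the data in view. The disagreement in step 4 is large enough for that choice to matter to the caution on the hazard ratio, which the crossing clause in Section 10.4 does not supply. The SAP points to appendices for imputation and for the Bayesian model, but not here. For a shape without a crossing, Section 10.4 helps less: with waning benefit (HR 0.6 to year 2, then 1.0), neither trigger fires in 1 − 0.680 − 0.048 = 27% of trials with linear time.

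The missing detail stands, and adding it would do no harm. The rest is weaker. Section 10.4.2 is incomplete rather than empty: it names the model term and requires significance, Section 10.2 makes testing two-sided, and 0.05 is the level used for endpoints. The log-log plots do not require choosing a time function for the interaction, although they have no decision rule. Disagreement between the triggers is not a defect, because crossing describes the observed curves and the interaction tests proportionality; either can suffice. Nowhere does the SAP treat a crossing as proof of non-proportional hazards.

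**Conclusion.** No change is needed. Followed as written, the plan gives a fixed primary test and a full set of yearly estimates whichever trigger fires. Type I error for the primary endpoint is unaffected. The freedom that remains concerns emphasis and one sentence of caution.

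In the shape that prompts the concern, an early INV excess with later benefit, the two routes together miss about 0.2-6% of trials, or 1-12% under the stricter crossing definition. In those trials the yearly table still shows the pattern. Chance crossings when there is no effect mean only that results already tabulated get more discussion.

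The simulated figures rest on assumed event rates, effect shapes and uniform accrual, and on unadjusted models without competing death. A value for large would make the test fire less often. The argument that the primary result does not depend on the triggers comes from the SAP text and needs none of these assumptions. The choice of time function is a trade-off between sensitivity to early and to late departures, which analysts can settle and report.
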